## Phase 2 AIM 2 (Enhanced Intervention Evaluation)

- a) To assess the relative effectiveness of two strategies for augmenting the It's weWomen Plus intervention (text messaging only or a combination of text and phone) on safety, mental health and empowerment outcomes among the non-responders.
- b) To compare the non-responder group of women to the responder group to determine if the strategies of augmentation brought the non-responders to the level of the responders on safety, mental health and empowerment
- c) To pilot test a gun safety intervention with a sub-sample of 55women who reported partner's ownership or access to a gun and compare their outcomes to 55 women who reported partner's ownership or access to a gun who did not receive the gun safety intervention

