#### c. Statistical plan including sample size justification and interim data analysis.

Based on results from our prior Risk Assessment Validation Study, we expect 30% of women to be non-responders (e.g., increase in severity and frequency of IPV) in the It's weWomen Plus intervention arm. Assuming an 80% retention rate at 12 months, we determined the sample per group needed to detect an effect is of .25 or greater. The addition of the phone component will focus on multiple issues using evidence-based approaches to interaction whereas the text messaging is tailored to the safety plan only. The phone-based intervention will allow more rapport building and personalized care via interaction with a trained interventionist using strengths-based approaches, so we expect an effect size in the small to moderate range (Cohen's d' of .2-.4). Interventions drawing from SMART design/SMART interventions may be powered similar to a standard RCT, if stage-specific questions (e.g., a comparison of first-stage interventions averaging over response and second stage interventions) are of primary interest and embedded dynamic treatment regimen development is of secondary interest. With power = 0.80, alpha = 0.05, and N=253 per group, we will be able to detect significant differences in the change over time between the two groups when the effect size is 0.25 or greater. This will require a total sample size of N=1,266 with 633 randomized to the It's weWomen Plus

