To identify and understand factors related to response/non-response to the It's weWomen Plus intervention will be tested among those randomly assigned to the It's weWomen Plus intervention group. Logistic regression will be used to identify baseline variables related to response/non-response. We will examine 2 indicators of response (safety and empowerment). For safety, non-response will be defined as no change or an increase in severity and frequency of IPV at follow-up; for empowerment non-response will be defined as no improvement in empowerment scores (at least a 0.25 standard deviation increase in scores) from baseline to follow up. Predictors of response will include demographic factors of age, race, marital status, and time in the US; risk factors (i.e., attitudes towards violence against women, discrimination, previous experience of IPV), and social support. Results from these analyses will be triangulated with results for the qualitative analyses to identify key factors for tailoring in future implementation of the intervention. To assess the relative effectiveness of two strategies for augmenting the It's weWomen Plus online intervention on safety, mental health and empowerment outcomes among the non-responders, Generalized Estimating Equations (GEE) with robust variance estimation will be used. Variables in the model include time (baseline and 12 months) and group which will have two levels: It's weWomen Plus online intervention and the addition of text messaging and It's weWomen Plus online intervention and text messaging and phone contact. Baseline variables on which the groups are not balanced by randomization will be included as covariates. The parameter of interest is the group by time interaction which will determine if the change over time in the outcome variables differs between the two groups. We will conduct sensitivity analyses including baseline variables found to predict intervention response and dose of the initial intervention. Dose will be captured by the number and duration of prescribed sessions/timepoints of intervention completed, number of and duration of unprescribed sessions (i.e., woman visiting intervention website outside the prescribed time points) and receipt of usual care services. These variables will be added to the GEE models described above to determine if significant differences in change over time remain controlling for predictors of non-response and dose of the initial intervention. Similarly, to determine if the strategies of augmentation brought the non-responders to the level of the responders on outcomes, GEE also will be used controlling for baseline variables on which the groups are not balanced by randomization. In this analysis there will be four groups: responders to usual care control arm and responders to the It's weWomen Plus online intervention, the It's weWomen Plus online intervention and the addition of text messaging and the It's weWomen Plus online intervention and text messaging and phone contact. Responders will be coded as the reference group in order to compare responders to the two groups of non-responders that received augmentation. Once again, the group by time interaction will be the parameter of interest to determine if the change over time in the outcomes differs between the responders and those receiving either adaptive intervention. We will use the 'weighted and replicated' estimation

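### Aim 2b asks whether augmented non-responders reached the responders' level, but the plan offers only a test of difference and no rule by which parity could be shown

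*Combined protocol and SAP*

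**What the plan says.** Section 2, Phase 2 Aim 2b, compares non-responders with responders "to determine if the strategies of augmentation brought the non-responders to the level of the responders on safety, mental health and empowerment". Section 7c carries the question into the analysis plan as "to determine if the strategies of augmentation brought the non-responders to the level of the responders on outcomes".

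The method in section 7c is a GEE with four groups: responders in usual care, responders to the online intervention, and the two augmentation strategies. On coding it says: "Responders will be coded as the reference group in order to compare responders to the two groups of non-responders that received augmentation". On the criterion it says: "Once again, the group by time interaction will be the parameter of interest", the purpose being "to determine if the change over time in the outcomes differs between the responders and those receiving either adaptive intervention".

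Sections 7a to 7c give no equivalence or non-inferiority margin, no confidence-interval criterion and no rule for concluding that the level was reached. The stated sample size, "With power = 0.80, alpha = 0.05, and N=253 per group", is for detecting a difference in change between two groups "when the effect size is 0.25 or greater". No power is stated for Aim 2b.

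**The concern.** The aim is a claim that one group is no worse than another. The null hypothesis of the planned test is that the groups do not differ, so a significant result can only answer no (or show the augmented group doing better). To answer yes in the ordinary sense of having caught up, an analyst following the plan has only a non-significant interaction to point to.

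That reverses the usual incentive: smaller groups and heavier dropout widen the interval and make a non-significant result more likely. This matters here because section 4a reports poor retention in the preceding study. At stake is a statement, covering the primary outcome of physical violence (section 7a), that text or phone support closes the gap for women who did not respond at first, when a real gap may remain.

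**Working it through.** **The plan's own figure.** For a two-sided 5% test, 80% power and 0.25 SD, n = 2(1.96 + 0.842)²/0.25² = 251.2, so 252 per group; the t-based value is 252.1, so 253. This matches section 7c. The 253 is also the number re-randomised to each strategy: (0.30 × 633)/2 + (0.50 × 633)/2 = 94.95 + 158.25 = 253.2. It concerns a difference between two groups, not Aim 2b.

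**Inputs for Aim 2b (all from section 7c).**
- One augmentation strategy: 95 + 158 = 253 re-randomised; 0.8 × 253 = 202 completers.
- Online-arm responders: 633 − 190 = 443; 0.8 × 443 = 354.
- Usual-care responders: 633 − 316 = 317; 0.8 × 317 = 253 (253.6 rounded down; its match with the 253 above is chance).
- All responders: 443 + 317 = 760; 0.8 × 760 = 608.

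The text does not settle whether the reference is one responder group or both, so all three are shown.

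**Formulas (outcome SD of 1 on the change scale, independent groups, normal approximation).**
- SE = √(1/n₁ + 1/n₂).
- Probability of a non-significant result under a true shortfall d: 1 − [Φ(d/SE − 1.96) + Φ(−d/SE − 1.96)].
- Probability of showing non-inferiority with margin m and no true shortfall: Φ(m/SE − 1.96).

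Example, all responders: SE = √(1/608 + 1/202) = 0.0812. With d = 0.20, d/SE = 2.463 and Φ(2.463 − 1.96) = 0.692 (the other tail is negligible), so 30.8% of trials are non-significant.

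| Reference group (completers) v 202 | SE | 95% CI half-width | Non-significant: d = 0.10 | d = 0.15 | d = 0.20 | d = 0.25 |
|---|---|---|---|---|---|---|
| All responders (608) | 0.0812 | 0.159 | 76.6% | 54.5% | 30.8% | 13.2% |
| Online-arm responders (354) | 0.0882 | 0.173 | 79.5% | 60.2% | 37.9% | 19.1% |
| Usual-care responders (253) | 0.0944 | 0.185 | 81.5% | 64.4% | 43.7% | 24.5% |

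**Effect of precision.** With no dropout and all responders (760 v 253, SE 0.0726), the figures at 0.20 and 0.25 SD are 21% and 7%, against 31% and 13% at 80% retention. If retention were 60% (my assumption; 0.6 × 443 = 266 online-arm responders v 0.6 × 253 = 152), they would be 50% and 31%, against 38% and 19%.

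**What a confidence-interval rule would give.** The documents state no margin, so a range is shown, with no true shortfall.

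| Reference group | m = 0.25 | m = 0.20 | m = 0.10 |
|---|---|---|---|
| All responders | 86.8% | 69.2% | 23.3% |
| Online-arm responders | 80.9% | 62.1% | 20.4% |
| Usual-care responders | 75.5% | 56.3% | 18.4% |

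**The case against.** **The misreading is not written down.** A reader might infer that the plan will treat a non-significant interaction as parity. No section says so. The GEE yields an estimate and an interval, and the authors could report that no difference was detected and show the interval. That stands. What remains is that the plan gives no rule for an affirmative answer.

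**Worse figures can be produced, but not for a planned contrast.** Restricting to online-arm non-responders (95 per strategy, 76 completers) against 354 online-arm responders gives non-significance rates of 65% at 0.20 SD and 49% at 0.25 SD. Section 7c defines the augmented groups by strategy, without a split by first-stage arm, so these figures should not be used to size the problem.

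**0.25 SD is not the plan's margin.** It is tempting to read it as the smallest effect of interest. Section 7c gives it as the detectable effect while expecting a Cohen's d of 0.2 to 0.4, so smaller effects are contemplated. Its other use is as an individual improvement cutoff for empowerment only; it is not a between-group margin, and it does not apply to violence, PTSD or depression.

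**Selection may matter more.** Section 4a defines responders by improvement from baseline to 3 months, and the interaction compares change from baseline. A gap in change is therefore partly built in, which favours detecting a shortfall: at 0.40 SD (354 v 202) only about 0.5% of trials would miss it. This limits how often false parity would arise and means the contrast is not randomised. It does not supply a rule for declaring parity when the gap is small.

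**Conclusion.** The concern holds in this form: Aim 2b poses a parity question, the plan tests only for a difference, and no margin or confidence-limit rule allows parity to be shown. For one augmentation strategy, a true shortfall of 0.20 SD would go undetected in 31% to 44% of trials and one of 0.25 SD in 13% to 25%, depending on the reference group.

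These figures assume unit SD, 80% retention in every group and independent groups, with no allowance for the weighting and replication in section 7c; weighting would probably widen the standard errors.

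This is a should-fix. A reader might think it undermines the trial's sample size, but the stated power is for a two-group difference, no power is claimed for Aim 2b, and the comparison of the two augmentation strategies in Aim 2a is untouched by this point.

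**What to change.** In section 7c, where the comparison with responders is described, state that:

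- a non-significant interaction is not evidence of parity;
- an augmented group will be said to have reached the responders' level only if the 95% confidence interval for its shortfall excludes a prespecified margin;
- the margin is set and justified separately for safety, mental health and empowerment before results are seen;
- if the interval excludes neither the margin nor zero, the estimate and interval are reported as inconclusive;
- the contrast is non-randomised, because responders are selected on improvement to 3 months, and will be reported as such.

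The plan should also say which responders form the reference, since the precision depends on it. A margin of 0.25 SD is an illustrative candidate only. With no true shortfall it would be met with a probability of about 75% to 87%; at 0.10 SD this falls to about 18% to 23%, so the choice of margin decides whether the aim can be answered with this sample.

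Model and data stay the same. The cost is the work of justifying a margin for each outcome, and accepting that some results will be inconclusive.

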intervention and 633 to usual care. With a 30% nonresponse rate, 190 women will be eligible to be randomized to It's weWomen Plus online intervention+text messaging or the It's weWomen Plus online intervention+ text messaging + phone contact with 95 per group. We expect a higher rate of non-responders in the control arm, with 50% of women (N=316) eligible for randomization into groups ( the It's weWomen Plus online intervention +Text Messages or the It's weWomen Plus online intervention + Text Messages +Phone Calls) with N=158 per group. Using the eligibility criteria of women aged 18 or older, foreign-born Latina, Asian or African, have experienced IPV in the past year, and have access to a safe computer/smartphone and are comfortable using it to access the study, we will recruit 1,266 women for the proposed study. In addition, we will recruit 55 women with abuser's access/ownership of firearm for pilot test of the gun safety booster intervention and compare it with 55 women with abuser's access/ownership of firearm in the main trial usual care control arm.

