
method that effects for the adaptive interventions can be simultaneously estimated in the same model. Inverse probability weighting for probability of receiving an adaptive intervention will be relative to the number of times an individual is randomized (e.g. responders have a weight of ½ and non-responders have a weight of ½). As observations need to be used in more than one comparison, data will be replicated. Sensitivity analyses will include dose of initial intervention (as described above) and baseline variables found to predict intervention response in Phase 1 as covariates in the models.

Potential Confounding Variables. T-test and chi-square tests will be used to examine if each randomization succeeded in creating balance on key demographic and baseline outcome variables. We will control for any variables that are found to be significantly different in the corresponding main analyses.

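### Covariates for the main GEE models are chosen by significance tests of baseline balance instead of being fixed in advance, and the Aim 2a model pools both first-stage arms without a term for arm

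*Combined protocol and SAP*

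**What the plan says.** All of this is in section 7c of the combined protocol and SAP.

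- **Selection rule.** The paragraph on potential confounding variables applies t-tests and chi-square tests after each randomisation to demographic variables and baseline outcomes, and then states: "We will control for any variables that are found to be significantly different in the corresponding main analyses". It gives neither the list of variables nor the test level.
- **Aim 2a model (text versus text plus phone, non-responders).** A GEE with robust variance: "Variables in the model include time (baseline and 12 months) and group which will have two levels". Baseline variables found to be unbalanced are added as covariates. The parameter of interest is the group-by-time interaction. First-stage arm is not listed.
- **Aim 2b model (responders versus augmented non-responders).** The same rule: "GEE also will be used controlling for baseline variables on which the groups are not balanced by randomization". Responders are split into two groups by first-stage arm. The augmented non-responders are split by augmentation only.
- **Who is pooled in Aim 2a.** From the intervention arm: "With a 30% nonresponse rate, 190 women will be eligible to be randomized". From the control arm: "with 50% of women (N=316) eligible for randomization into groups". That gives 95 + 158 = 253 women per second-stage group.
- **Sensitivity analyses only.** Baseline predictors of response, and dose of the initial intervention (which counts receipt of usual care services), are added to the models here.

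No covariate is fixed in advance for a main model, and the plan does not say whether covariates enter as main effects or also by time.

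**The concern.** After a sound randomisation, a significant baseline difference is a chance event. Selecting on it brings in variables because they happened to differ, whether or not they predict outcome, and usually leaves out the strong predictors. The fitted model is then unknown until the data are in.

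Three features of this plan add to that general point.

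- In Aim 2b the compared groups are formed by 3-month response. Asking whether randomisation balanced them does not address the confounding that this creates.
- The rule covers baseline outcomes. A flagged one would become a covariate in a model that already holds the same measurement as the response at the baseline time point.
- The estimand is a group-by-time interaction, so what a covariate does depends on how it enters. The plan leaves that open.

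Separately, Aim 2a pools women with different histories. Non-responders from the intervention arm have already had the online intervention. Those from the control arm first receive it together with the augmentation. One pooled estimate averages over these two situations. At stake are a main analysis that can be stated beforehand, precision that costs almost nothing to gain, and a clear reading of the Aim 2a result.

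**Working it through.** **1. The plan's own figure.** Inputs: "With power = 0.80, alpha = 0.05, and N=253 per group", for "differences in the change over time between the two groups when the effect size is 0.25 or greater". Two-sided testing is assumed, because the plan does not state sidedness.

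- n per group = 2(1.960 + 0.842)² / 0.25² ≈ 251.2, so 252. The t-based value is 252.1, which rounds up to 253.
- Power at 253: standard error √(2/253) = 0.0889; 0.25/0.0889 − 1.960 = 0.852; power 0.803.
- 190 + 316 = 506 = 2 × 253.

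The stated figure reproduces, and it belongs to the Aim 2a comparison.

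**2. How often the rule fires by chance.** P(at least one significant) = 1 − 0.95^k for k independent tests at 0.05. The plan gives neither k nor the level, so this is a range.

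| k | 4 | 8 | 10 | 14 |
|---|---|---|---|---|
| Chance per randomisation | 18.5% | 33.7% | 40.1% | 51.2% |

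**3. What a selected covariate does in the stated model.** With two time points, an identity link and complete data, the group-by-time coefficient is the difference between groups in mean within-woman change. A baseline covariate entered as a main effect has the same value at both times and cancels from the change. A simulated data set of 506 women, split 95/95 and 158/158, confirms this:

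| Model | Loss at 12 months | Estimate | Robust SE |
|---|---|---|---|
| Group × time | none | 0.1175 | 0.0932 |
| + baseline covariate, arm, or both, as main effects | none | 0.1175 | 0.0932 |
| + arm × time | none | 0.1175 | 0.0929 |
| Group × time | 20% | 0.1255 | 0.0993 |
| + baseline covariate and arm, as main effects | 20% | 0.1281 | 0.0996 |

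**4. Where precision can be gained.** The stated model is a change analysis. Adjusting the 12-month value for the baseline value has residual variance (1 − r²) against 2(1 − r) for change, a ratio of (1 + r)/2, where r is the baseline-to-12-month correlation (assumed). With 0.25 in units of the SD of change and 253 per group:

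| r | Variance ratio | Power, change | Power, baseline-adjusted | n per group for 80% |
|---|---|---|---|---|
| 0.3 | 0.65 | 0.803 | 0.937 | 164 |
| 0.5 | 0.75 | 0.803 | 0.901 | 189 |
| 0.7 | 0.85 | 0.803 | 0.862 | 214 |

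The plan does not say which SD its effect size uses. If it is the SD of the outcome, power goes from 0.661 to 0.838, 0.803 to 0.901, and 0.953 to 0.976 at the same three correlations.

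These figures take 253 per group as analysed. With 80% retained (0.8 × 253 ≈ 202) and the effect in change-SD units, 0.71 becomes 0.876, 0.827 and 0.778.

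**5. What first-stage arm adds.** The share of pooled women from the intervention arm is p = 190/506 = 0.375. For a difference δ between arms (assumed, in within-arm SD), the variance explained is R² = b/(1 + b) with b = p(1 − p)δ². The overall SD is set to 1 and the residual SD is √(1 − R²).

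| δ | R² | Power at 253 with arm (0.803 without) |
|---|---|---|
| 0.1 | 0.002 | 0.804 |
| 0.25 | 0.014 | 0.809 |
| 0.5 | 0.055 | 0.825 |
| 0.8 | 0.131 | 0.854 |

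**6. Check by simulation.** In 4,000 trials with r = 0.5 and an arm difference of 0.25 SD, power was 0.798 for the change analysis, 0.803 with arm, 0.898 with the baseline outcome and 0.902 with both. Nearly all of the gain comes from the baseline outcome.

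**The case against.** The best defence is that the selection rule does little harm to the stated estimate. Step 3 supports this. If covariates enter as main effects with an identity link, whichever ones the tests select, the Aim 2a interaction hardly moves. The plan also already looks at prognostic adjustment in its sensitivity analyses, with marital status and social support among the candidate predictors. Both points stand. The first is also a criticism of the plan, because an adjustment that cannot move the estimate cannot correct an imbalance. The invariance need not hold exactly under another link, and the links are not stated.

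A reader might infer more than the documents support:

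- **That test-then-adjust costs about 8 points of power.** A single-outcome model with 202 per group and a covariate explaining 20% of the variance does give 71.5% under the rule against 79.8% with fixed adjustment. That is not the plan's model, so neither this loss nor any shift in type I error can be attributed to the plan as written.
- **That first-stage arm is absent from every model.** It is absent from Aim 2a. Aim 2b defines its responder groups by arm, and dose with usual-care receipt is a partial stand-in in the sensitivity analyses.
- **That omitting arm biases Aim 2a or costs much precision.** With equal splits within each arm there is no bias, and the cost is under 1 power point for arm differences up to 0.25 SD.
- **That the plan's primary model is at stake.** The plan names a primary outcome (safety) but labels no model as primary. The sample size does match Aim 2a.

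**Conclusion.** The concern holds in this form. Main-model covariates are chosen by chance imbalance, so the models are not fixed in advance and prognosis plays no part in the choice. The chance that at least one variable enters is about 19% to 51% per randomisation, on the assumption of 4 to 14 independent tests at 0.05. In Aim 2b the rule cannot identify confounders, because the groups are not randomised. In Aim 2a, main-effect adjustment would leave the estimate unchanged under an identity link with complete data.

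Leaving first-stage arm out of Aim 2a is mainly a problem of interpretation. The precision that can be recovered lies in the baseline outcome: power of 0.86 to 0.94 instead of about 0.80 at 253 per group, for assumed correlations of 0.7 to 0.3 and the effect in change-SD units. This is a worthwhile, low-cost change to the plan. It does not show that the planned Aim 2a comparison is invalid.

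**What to change.** 1. Stop using balance tests to select covariates, and present baseline tables descriptively.
2. For Aim 2a, name the covariates now: the baseline value of the outcome, first-stage arm, and a short list chosen for prognosis (for example baseline PTSD and depression symptoms, relationship status, social support).
3. State how they enter, so that they adjust the 12-month contrast. The simplest form is ANCOVA on the 12-month outcome. If the two-time-point GEE is kept, the covariates need covariate-by-time terms. State the link for each outcome.
4. Show the Aim 2a estimate by first-stage arm as exploratory.
5. For Aim 2b, pre-specify prognostic covariates on subject-matter grounds and state that responder versus non-responder contrasts are non-randomised. Do not add arm as a covariate there. It already defines the responder groups, so its coefficient would come from the non-responders alone and would change the meaning of the responder contrasts. Covariates will not remove all of the confounding created by grouping on response.

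The cost is a few degrees of freedom and a change to the analysis wording before outcome data are seen. No new data are needed.
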